6.10.1.6 Sensor precision analysis

Sensor precision will be evaluated by paired absolute relative difference (PARD) and percent coefficient of variation (PCV). PARD is the absolute value of the Primary Sensor reading minus the paired Secondary Sensor reading divided by the average of the two Sensor readings. PCV is the standard deviation of the two paired Sensor readings divided by the average of the two paired Sensor readings. The mean values of PARD and PCV will be tabulated (Table 9 in APPENDIX 1).

$$\text{PARD} = \left(\left(\sum \frac{|\text{Glucose}_{\text{SENSOR 1}} - \text{Glucose}_{\text{SENSOR 2}}|}{(\text{Mean Glucose})_{\text{SENSOR 1 and 2}}} \right) / n \right) \times 100\%$$

$$\text{PCV} = \left(\left(\sum \frac{\text{SD of } (\text{Glucose}_{\text{SENSOR 1}} \text{ and } \text{Glucose}_{\text{SENSOR 2}})}{(\text{Mean Glucose})_{\text{SENSOR 1 and 2}}} \right) / n \right) \times 100\%$$

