I agree to conduct this clinical investigation in accordance with the design and specific provisions of this protocol and all applicable regulatory requirements. Modifications to the clinical investigation are acceptable only with a mutually agreed upon protocol amendment as approved by the sponsor, regulatory bodies and Institutional Review Board/ Ethics Committee. I agree to await Institutional Review Board/ Ethics Committee approval of the protocol, informed consent, and sponsor approval before initiating the study, and to obtain consent from subjects prior to their enrollment in the study. I agree to collect and record data as required by the protocol and case report forms, and to maintain study documents for the period of time required.

Confidential

This document contains confidential information belonging to Senseonics, Inc. Except as may be otherwise agreed to in writing, by accepting or reviewing these materials, I agree to hold such information in confidence and not to disclose it to others (except where required by applicable law), nor use it for unauthorized purposes.

Investigator's signature

Date of signature

SYNOPSIS

Title of Protocol	PRECISION Study: A Prospective , Multicenter Evaluation of Precision , Compression , Accuracy and Updated Algorithm of a Novel Continuous Implanted Glucose Sensor
Sponsor	Senseonics, Inc.
Investigational Device	Senseonics Continuous Glucose Monitoring (CGM) System (the "System")
Reference Instrument	Reference Glucose Analyzer (bedside, YSI 2300 STAT PLUS® Glucose and Lactate Analyzer, Yellow Springs Instruments, Yellow Springs, OH, USA).
Calibration Standard	FDA-cleared Blood Glucose Meter (Subject SMBG Meter)
Study Purpose	The purpose of this clinical investigation is to evaluate the precision and accuracy of the Senseonics Continuous Glucose Monitoring System (Senseonics CGM System) measurements when compared with reference standard measurements. Compression of the sensor site and use of a new algorithm will also be evaluated. The investigation will also evaluate safety of the Senseonics CGM System usage.

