11.3.2.7 Sensor precision analysis

Sensor precision will be evaluated by paired absolute relative difference (PARD) and percent coefficient of variation (PCV). PARD is the absolute value of the Primary Sensor reading minus the paired Secondary Sensor reading divided by the average of the two

Sensor readings. PCV is the standard deviation of the two paired Sensor readings divided by the average of the two paired Sensor readings. The mean values of PARD and PCV will be tabulated (Table 9 in APPENDIX 1).

$$\text{PARD} = \left(\left(\sum \frac{|(\text{Glucose})_{\text{SENSOR 1}} - (\text{Glucose})_{\text{SENSOR 2}}|}{(\text{Mean Glucose})_{\text{SENSOR 1 and 2}}} \right) / n \right) \times 100\%$$

$$\text{PCV} = \left(\left(\sum \frac{\text{SD of } (\text{Glucose})_{\text{SENSOR 1 and 2}}}{(\text{Mean Glucose})_{\text{SENSOR 1 and 2}}} \right) / n \right) \times 100\%$$

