6.10 Exploratory Effectiveness Endpoint

Exploratory effectiveness measures are discussed in this section. Only descriptive statistics will be provided for these exploratory outcomes. All analyses will be provided as described below and by clinic visit day. SMBG glucose values may also be used as reference for some of these analyses.

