		Percent 15/15% of Reference	Percent 20/20% of Reference	Percent 30/30% of Reference	Percent 40/40% of Reference	Percent Greater than 40/40% of Reference
Overall						
< 70						
70-180						
>180						

Table 7A. Concurrence of CGM System Readings and YSI Values within YSI Glucose Ranges (Sample Table)

YSI (mg/dL)	Number of Paired CGM-YSI (n)	Percent of Matched Pairs in Each CGM System Glucose Range for Each YSI Glucose Range								
		CGM (mg/dL)								
<40										
40-60										
61-80										
81-120										
121-160										
161-200										
201-250										
251-300										
301-350										
351-400										
>400										

Table 7B. Concurrence of CGM System Readings and YSI Values within CGM System Ranges (Sample Table)

CGM (mg/dL)	Number of Paired CGM-YSI (n)	Percent of Matched Pairs in Each YSI Glucose Range for Each CGM Glucose Range YSI (mg/dL)									
		<40	40-60	61-80	81-120	121-160	161-200	201-250	251-300	301-350	351-400
40-60											
61-80											
81-120											
121-160											
161-200											
201-250											
251-300											
301-350											
351-400											

Table 8. CGM System Accuracy by Visit Number (Sample Table)

Day Number	Number of Paired CGM-YSI	Mean Absolute Relative Difference (%)	Median Absolute Relative Difference (%)	Percent of CGM System Readings Within				
				Percent 15/15% of Reference	Percent 20/20% of Reference	Percent 30/30% of Reference	Percent 40/40% of Reference	Percent Greater than 40/40% of Reference
Day 1								
Day 7								
Day 14								
Day 30								
Day 60								
Day 90								

Table 9. CGM System between System Precision (Sample Table)

Level of Mean Glucose (mg/dL)	Mean Difference (Sensor 1 - Sensor 2) (mg/dL)	SD of Difference (mg/dL)	N Pairs
<= 70			
71-180			

Level of Mean Glucose (mg/dL)	Mean Difference (Sensor 1 - Sensor 2) (mg/dL)	SD of Difference (mg/dL)	N Pairs
> 180			
All			
PARD			
PCV			

Table 10A. CGM System Performance during Sleep Challenges (Sample Table)

Night Time (Y/N)	Number of Paired CGM-YSI	Mean Absolute Relative Difference (%)	Median Absolute Relative Difference (%)	Percent of CGM System Readings Within				
				Percent 15/15% of Reference	Percent 20/20% of Reference	Percent 30/30% of Reference	Percent 40/40% of Reference	Percent Greater than 40/40% of Reference
Y								
N								

Table 10B. CGM System between System Precision during Sleep Challenges (Sample Table)

[figure not shown]
Night Time (Y/N)	N Pairs	PARD
Y		
N		

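### PCV as defined equals PARD divided by √2 and, read as the between-sensor CV, is about 20% too low under normal errors with a common CV

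*SAP*

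**What the plan says.** The Protocol synopsis states the study purpose in these terms: "The purpose of this clinical investigation is to evaluate the precision and accuracy" of the CGM system against reference. Compression, a new algorithm and safety follow.

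The precision analysis is in SAP 6.10.1.6 and, with the same definitions, in Protocol 11.3.2.7. For each pair of simultaneous readings, "PARD is the absolute value of the Primary Sensor reading minus the paired Secondary Sensor reading divided by the average of the two Sensor readings", and "PCV is the standard deviation of the two paired Sensor readings divided by the average of the two paired Sensor readings". Both formulas sum the pair values and divide by the number of pairs, and the text confirms it: "The mean values of PARD and PCV will be tabulated". Neither document states whether the SD uses divisor n-1 or n, and neither mentions any relation between the two measures.

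Sample Table 9 has one PARD row and one PCV row. It also gives the mean and SD of the Sensor 1 minus Sensor 2 difference in mg/dL, with the number of pairs, by glucose level and overall. On status, SAP 6.10 says: "Only descriptive statistics will be provided for these exploratory outcomes".

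**The concern.** Two named statistics suggest two views of precision, and the second is called a coefficient of variation. Most readers will take that to mean the between-sensor SD as a percentage of the mean. With only two readings per pair, the SD is a rescaled absolute difference, so PCV repeats PARD. Averaging such SDs, rather than their squares, also gives a number below the CV that the label suggests.

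The analysis has no hypothesis test or acceptance limit, so the printed figure is the whole result. If it is read as a CV, the device looks more precise than the paired data show. Averaging also hides uneven performance, because a mixture of good and poor pairs can give the same PCV as uniform pairs.

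**Working it through.** The documents give no expected PCV or precision target, so there is no planned figure to reproduce. All CVs, offsets and error shapes below are assumptions.

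**Inputs.** The PARD and PCV definitions and the arithmetic averaging come from SAP 6.10.1.6 and Protocol 11.3.2.7. Two-sensor subjects number 36 - 9 = 27 to 36 - 6 = 30 (SAP 4.4). The left sensor is linked to Gen 1 and the right to Gen 2 (SAP 3).

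**Step 1: identity.** Let d = S1 - S2 and m = (S1 + S2)/2. The n-1 SD of two values is |d|/√2. For every pair, PCV = |d|/(√2 × m) = PARD/√2, and the same holds for the means.

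| Pair (mg/dL) | PARD | PCV | PARD/PCV |
|---|---|---|---|
| 100, 120 | 18.18% | 12.86% | 1.4142 |
| 55, 70 | 24.00% | 16.97% | 1.4142 |
| 300, 260 | 14.29% | 10.10% | 1.4142 |

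**Step 2: expected size.** With independent normal errors and a common CV c, d/m is approximately normal with mean 0 and variance 2c². Then E(PCV) = c × √(2/π) = 0.798c, a shortfall of 1 - 0.798 = 20.2%. The comparator is the root-mean-square (RMS) within-pair CV, √[(1/n) × Σ d²/(2m²)]. An arithmetic mean of non-negative values never exceeds their RMS, so PCV can never be above it.

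**Step 3: simulation.** Each scenario used 2,000,000 pairs with glucose uniform on 60-350 mg/dL. Ratios were taken before rounding.

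| Assumed errors | PCV | RMS CV | PCV/RMS |
|---|---|---|---|
| Normal, CV 5% | 3.99% | 5.01% | 0.798 |
| Normal, CV 10% | 8.01% | 10.07% | 0.796 |
| Normal, CV 20% | 16.30% | 20.66% | 0.789 |
| Uniform, CV 10% | 8.19% | 10.03% | 0.816 |
| t with 5 df, CV 7% | 5.32% | 7.09% | 0.751 |
| Laplace, CV 8% | 6.04% | 8.11% | 0.745 |
| Half CV 5%, half CV 15% | 8.05% | 11.36% | 0.709 |
| Normal, CV 10%, arm offset 5% | 8.52% | 10.69% | 0.797 |
| Normal, CV 10%, arm offset 10% | 9.95% | 12.35% | 0.806 |
| Normal, CV 10%, arm offset 20% | 14.92% | 17.45% | 0.855 |

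The shortfall against RMS runs from 15% to 29%. A separate simulation gave each of 27 or 30 subjects persistent sensor offsets (SD 8%) plus noise (6%). The mean ratio was 0.801, with 95% of runs between 0.77 and 0.82.

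**Step 4: masking.** With half the pairs at CV 6% and half at 14%, the expected PCV is 0.798 × (6 + 14)/2 = 8.0%, the same as if every pair had CV 10%. The RMS CV is √[(6² + 14²)/2] = 10.8%.

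**The case against.** The strongest reply is that nothing is miscalculated. PCV is defined in words and in a formula, and neither document presents it as an estimate of a population CV. That stands: the shortfall exists only when PCV is read as the between-sensor CV. It is nevertheless the natural reading of the name, and neither document warns against it.

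A second reply is that Table 9 already gives the SD of the difference, which is built from squares. Divided by √2, it gives a between-sensor SD free of this bias. That also stands, but the result is in mg/dL and does not correct the PCV row.

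A third reply is that RMS is not simply the true CV. It absorbs any systematic Gen 1 versus Gen 2 offset: with random CV 10% and a 10% offset it is 12.35%, while PCV is 9.95%, close to the random part. It also reacts more to dropouts. If 2% of pairs had one sensor reading 50% low (assumed), RMS would rise from 10.1% to 12.0% and PCV from 8.0% to 8.8%. Both points are right, and they are reasons to print both figures and read them with the mean difference.

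A reader might go further and infer that the SD could be computed with divisor n, which would make PCV equal to PARD/2 and about 44% low. The documents leave the divisor open, but nothing in them points to n. This supports stating the divisor, not claiming that size of error.

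**Conclusion.** The point holds in a limited form. Given the n-1 SD, the identity PCV = PARD/√2 is exact and needs no assumption about the data. The 20% shortfall rests on normal errors, a common CV and little systematic offset; 15-29% covers the other scenarios tried. The direction is fixed when the target is the RMS within-pair CV, which includes any offset between arms. If the target were random sensor error alone, a large offset could put PCV above it, as the 20% offset row shows (14.92% against 10%).

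A reader might infer that the study's main result is compromised because precision comes first in the stated purpose. The documents do not support that. Precision is one of several purposes, the effectiveness endpoint is MARD, the precision analysis is listed as exploratory in SAP 4.2.3, and no decision or sample size depends on PCV. MARD, PARD, the SD of the difference and the night-versus-day precision comparison in Table 10B, which uses PARD only, are unaffected. What remains is one device-favourable number in the precision table under a label that it does not meet.

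**What to change.** In SAP 6.10.1.6, Protocol 11.3.2.7 and Table 9 of both appendices:

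- Report the overall within-pair CV as 100% × √[(1/n) × Σ (S1 - S2)²/(2 × mean²)], where mean is the average of the two readings in the pair.
- Keep the existing figure beside it, labelled *mean two-reading CV = PARD/√2, n-1 SD*. This states the divisor and shows that the figure repeats PARD.
- Add a note that the RMS CV includes any systematic difference between the Gen 1 (left) and Gen 2 (right) systems and should be read with the mean difference already in Table 9.

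The change should be made before the data submission planned on results through Visit 6. It costs one formula, one table row and one note, with no new data. The downside is a less favourable precision figure that is more sensitive to outlying pairs. Reporting it by glucose level is optional and would need a change to the table layout, since PCV is now a single row.

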6.10.1.7 Effect of compression on sensor performance during sleep challenges

For the sleep assessment periods during visits 4 & 5, compression may occur to the sensor site when the subject is sleeping at night. The system's difference and agreement with reference and between system precision will be compared between the night time and the day time (Tables 10A and 10B in APPENDIX 1).

6.10.1.8 Mean Absolute Difference between sensor and reference measurements for reference values less than or equal to 80mg/dL

The mean absolute difference (MAD) for reference glucose values less than or equal to 80 mg/dL is defined as the absolute difference of paired Senseonics CGM System and Reference readings for reference glucose values ≤ 80 mg/dL.

$$MAD = \left(\sum |(Glucose)_{SENSOR} - (Glucose)_{REFERENCE}| \right) / n$$

This analysis will quantify both cumulative results as well as stability over time in 30 day intervals (Tables 11A and 11B in APPENDIX 1).

6.10.1.9 Mean Absolute Difference between sensor and reference measurements for system full scale range (40-400mg/dL)

$$MAD = \left(\sum |(Glucose)_{SENSOR} - (Glucose)_{REFERENCE}| \right) / n$$

This analysis will quantify both cumulative results as well as stability over time in 30 day intervals (Tables 11A and 11B in APPENDIX 1).

6.10.1.10 Mean Relative Difference (%) for system full scale range (40-400mg/dL)

$$MRD = \left(\left(\sum \frac{(Glucose)_{SENSOR} - (Glucose)_{REFERENCE}}{(Glucose)_{REFERENCE}} \right) / n \right) \times 100\%$$

This analysis will quantify both cumulative results as well as stability over time in 30 day intervals (Tables 11A and 11B in APPENDIX 1).

6.10.1.11 Median Absolute Relative Difference for system full scale range (40-400 mg/dL)

$$\text{Median ARD} = \text{Median} \left(\left(\frac{|(Glucose)_{SENSOR} - (Glucose)_{REFERENCE}|}{(Glucose)_{REFERENCE}} \right)_i \right) \times 100\%, \quad i = 1, 2, \dots, n$$

This analysis will quantify both cumulative results as well as stability over time in 30 day intervals (Tables 11A and 11B in APPENDIX 1).

6.10.1.12 Median Absolute Difference between sensor and reference measurements

$$\text{Median AD} = \text{Median} (|(Glucose)_{SENSOR} - (Glucose)_{REFERENCE}|_i), \quad i = 1, 2, \dots, n$$

This analysis will quantify both cumulative results as well as stability over time in 30 day intervals (Tables 11A and 11B in APPENDIX 1).

6.10.1.13 Median Relative Difference between sensor and reference measurements

$$\text{Median RD} = \text{Median} \left(\left(\frac{(Glucose)_{SENSOR} - (Glucose)_{REFERENCE}}{(Glucose)_{REFERENCE}} \right)_i \right) \times 100\%, \quad i = 1, 2, \dots, n$$

This analysis will quantify both cumulative results as well as stability over time in 30 day intervals (Tables 11A and 11B in APPENDIX 1).

6.10.1.14 Clarke Error Grid Analyses

The glucose accuracy will be assessed using the Clarke Error Grid Analysis (EGA; Figure 2 in APPENDIX 1) (Clarke et al.¹⁵). The EGA takes into account not only the difference between the system-generated and reference blood glucose values but also the clinical significance of this difference. The grid breaks down a scatterplot of a reference glucose meter and an evaluated glucose meter into five regions:

1. Region A contains values within 20% of the reference Sensor,
2. Region B contains values that are outside of 20% but would not lead to inappropriate treatment,
3. Region C contains values leading to unnecessary overcorrection in treatment,
4. Region D contains values indicating a potentially dangerous failure to detect hypoglycemia or hyperglycemia, and
5. Region E contains values that could lead to errors in treatment of hypoglycemia for hyperglycemia and vice-versa.

The Clarke Error Grid Analysis will be provided by reference glucose level (Table 12 in APPENDIX 1). Percent of measures in the clinical accuracy Zone A will be estimated along with 95% confidence interval.

6.10.1.15 Consensus Error Grid Analyses

Accuracy of Senseonics CGM System versus reference glucose measures will also be summarized using the consensus error grid analysis.¹² (Figure 3 and Table 13 in APPENDIX 1). The revised error grid was based on a survey of a large number of experts (100 endocrinologists) and it retains the 5-risk level format of Clarke EGA. The improved grid has slightly altered the definitions of the risk levels so as to decouple them from the specific assumptions of the Clarke Error Grid.

6.10.1.16 Evaluation of glucose alert performance

The glucose alert performance of the Senseonics CGM System will be evaluated retrospectively on Senseonics CGM and reference measurements collected to determine accuracy of hypo- and hyperglycemic states and associated sensitivity and specificity (Tables 14A and 14B in APPENDIX 1). All rates are calculated assuming both threshold and 10-min ahead predictive alerts are turned on. Only performance against YSI is evaluated. For the alert performance evaluation, the following definitions will be used.

Hypoglycemia Alert Rate:

The Alert Rate shows how often the alert was right or wrong. The True Alert Rate is the % of time the device alerted when the blood glucose level was at or below the hypoglycemia alert setting

within 15 minutes before or after the device alerted. The False Alert Rate is the % of time the device alerted when the blood glucose level was above the hypoglycemia alert setting within 15 minutes before or after the device alerted.

Hypoglycemia Detection Rate:

The Detection Rate shows how often the device recognized and alerted that there was an episode of hypoglycemia or how often it missed such an event. The Confirmed Event Detection Rate is the % of time the blood glucose level was at or below the hypoglycemia alert setting and device alerted within 15 minutes before or after the blood glucose was at or below the alert settings. The Missed Event Detection Rate is the % of time the blood glucose was at or below the hypoglycemia alert setting, but the device did not alert within 15 minutes before or after the blood glucose was at or below the alert setting.

Hyperglycemia Alert Rate:

The Alert Rate shows how often the alert was right or wrong. The True Alert Rate is the % of time the device alerted when the blood glucose level was at or above the hyperglycemia alert setting within 15 minutes before or after the device alerted. The False Alert Rate is the % of time the device alerted when the blood glucose level was below the hyperglycemia alert setting within 15 minutes before or after the device alerted.

Hyperglycemia Detection Rate:

The Detection Rate shows how often the device recognized and alerted that there was an episode of hyperglycemia or how often it missed such an event. The Confirmed Event Detection Rate is the % of time the blood glucose level was at or above the hyperglycemia alert setting and the device alerted within 15 minutes before or after the blood glucose was at or above the alert settings. The Missed Event Detection Rate is the % of time the blood glucose was at or above the hyperglycemia alert setting, but the device did not alert within 15 minutes before or after the blood glucose was at or above the alert setting.

6.10.1.17 Deming regression analysis

The glucose readings of Senseonics CGM System versus reference glucose reference will be analyzed using the Deming regression (Figure 4 in APPENDIX 1). Deming regression (Deming18) is an errors-in-variables linear model for a two-dimensional dataset. It differs from the simple linear regression in that it accounts for errors in observations on both variables. Parameter estimates will be provided for the Deming regression coefficients including slope, intercept as well as correlation coefficient.

6.10.1.18 Bland Altman analysis

A Bland Altman plot analysis will compare the difference in readings between the Sensor and reference glucose to the average of the two readings across the accuracy evaluation period (Figure 5 in APPENDIX 1).

6.10.1.19 Kaplan-Meier Analysis of Sensor Survival

The Kaplan-Meier¹³ survival analysis will be used for assessing sensor life (Table 15 and Figure 6 in APPENDIX 1). Only sensors with sensor retirement alert triggered will be considered having reached end of life. Sensors with subject withdrawal or transmitter failure will be considered censored¹³.

6.10.1.20 Effect of gender on sensor performance

Sensor Agreement will be stratified by gender and examined to determine whether there is any evidence of differences between genders (Table 16 in APPENDIX 1).

6.10.1.21 Effect of age on sensor performance

Sensor Agreement will be stratified by the target age enrollment categories and examined to determine whether there is any evidence of differences between groups (Table 17 in APPENDIX 1).

6.10.1.22 Effect of BMI on sensor performance

Sensor Agreement will be stratified by the target BMI enrollment categories and examined to determine whether there is any evidence of differences between groups (Table 18 in APPENDIX 1).

6.10.1.23 Effect on sensor performance in dominant or non-dominant arm

Sensor Agreement will be stratified by dominant arm and examined to determine whether there is any evidence of differences (Table 19 in APPENDIX 1).

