4.1 Visit 1 – Screening/Enrollment

Subjects will be enrolled into the study following informed consent. Screening evaluation will determine subject eligibility for sensor insertion. No study-specific procedures may be performed prior to informed consent signature. The Screening Visit is anticipated to last approximately 2 hours. The visit will occur within 30 days before the Sensor Insertion Visit (V2).

The Screening Visit includes performing/collecting the following information:

- Demographics- including age, gender at birth, race/ethnicity, dominant hand, and BMI.
- Diabetes History- including type of diabetes, date of diagnosis or length of diabetes, history of DKA and severe hypoglycemia, current treatment (type of insulin and type of insulin delivery (injections or insulin pump), insulin doses, and when applicable: basal rates, correction factors, glucose targets, insulin duration, insulin to carbohydrate ratios, sliding scales).
- Current and Past Medical History- including concomitant medications.
- Physical examination and vital signs- including height, weight, blood pressure, pulse, temperature, assessment of potential sensor insertion sites, assessment of venous access for repeated blood draws.
- EKG- an EKG will be performed with the results kept in the subject records.
- Laboratory

Blood samples (approximately 6 ml total) will be drawn for the following laboratory tests.

All samples will be collected and processed as described in the operations manual:

- Hemoglobin A1C
- Dexamethasone

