11.1.4 Expected Paired Points by Range*

The expected number of paired YSI/sensor points by YSI glucose range are as follows:

YSI range	Each Day 1, 7, 14 16 Hr. Session	Each Day 30,60,90 12.5 Hr. Session	Total
40-60 mg/dL	166	106	815
61-80 mg/dL	446	285	2194
80-120 mg/dL	1128	722	5550
121-160 mg/dL	1078	690	5303
160-200 mg/dL	712	456	3505
201-250 mg/dL	620	397	3052
251-300 mg/dL	290	186	1426

301-350 mg/dL	127	81	623
350-400 mg/dL	65	42	319
		Total paired points	22786

*Estimates based on 66 sensors. Number of YSI values in each range will be approximately half the number of paired points.

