3 STUDY DESIGN

This is a non-randomized, prospective, single-arm, multi-center study, whereby approximately 44 subjects will be enrolled and 36 subjects will be inserted in the United States at up to 4 sites. The investigation will include both clinic visits and home use of the Senseonics CGM System. The subjects will have one or two Sensors inserted by trained Investigators. The Sensors will be inserted in the upper arms of the subjects. The accuracy of the Senseonics CGM System will be evaluated during clinic visits comparing Sensor glucose values and plasma glucose values measured on a bedside glucose analyzer. For qualifying subjects, during the clinic visits, there will be planned hyperglycemia and hypoglycemia challenges. Effects of compression/sensor dropout will be evaluated during the designated overnight periods.

In this study, including the clinic and home settings, all diabetes care decisions will be based on SMBG blood glucose values and clinical standard of care, rather than Senseonics CGM System results.

This study will not be randomized. Subjects will be selected consecutively (i.e., selecting every subject in the order they present at the site) among those who meet the

inclusion/exclusion criteria.

The Subject visit schedule includes 9 visits over a period of approximately 4.5 months (inclusive of visit windows from screening visit through follow-up visit). A subset of a minimum of 6 and a maximum of 9 subjects will have blood samples drawn daily for the first 7 days of sensor wear for additional dexamethasone screening and to determine blood draw time points during the first week of sensor wear for the remaining subjects. These subjects will only have one sensor inserted in the left arm, which will be linked to the Gen 1 transmitter. Remaining subjects will have 2 sensors inserted, one in each arm, with the left sensor linked to a Gen 1 transmitter, and the right sensor linked to the Gen 2 transmitter. These subjects may be required to make additional visits for dexamethasone screening between visits 3 and 4.

The study is anticipated to take approximately 6 months, including the enrollment period.

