4.3 Randomization

Subjects will not be randomized. Subjects will be selected consecutively (i.e., selecting every subject in the order they present at the site) among those who meet the inclusion/exclusion criteria.

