4.4 Sample Size Determination

Approximately 44 subjects will be enrolled and 36 subjects will be inserted with either one Sensor (dexamethasone sub-group of 6 to 9 subjects) or two Sensors in the clinical investigation. The sample size is not based on any power analysis but was agreed upon by the FDA to satisfy FDA's request for additional data to assess accuracy at different time points through day 30 and to obtain additional plasma levels of dexamethasone using a limit of detection of 50 pg/ml.

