Table 16. Effect of Gender on System and Reference Agreement (sample table)

Gender	Number of Paired Senseonics CGM and Reference	Percent within 20/20% Reference	Percent within 30/30% Reference	Percent within 40/40% Reference
M				
F				

Table 17. Effect of Age on System and Reference Agreement (sample table)

Age	Number of Paired Senseonics CGM and Reference	Percent within 20/20% Reference	Percent within 30/30% Reference	Percent within 40/40% Reference
18-20				
21-44				
45-65				
Over 65				

Table 18. Effect of BMI on System and Reference Agreement (sample table)

BMI	Number of Paired Senseonics CGM and Reference	Percent within 20/20% Reference	Percent within 30/30% Reference	Percent within 40/40% Reference
< 25				
[25, 30)				
≥ 30				

Table 19. Effect of Dominant Hand on System and Reference Agreement (sample table)

Dominant Hand (Y/N)	Number of Paired Senseonics CGM and Reference	Percent within 20/20% Reference	Percent within 30/30% Reference	Percent within 40/40% Reference
Y				
N				

Table 20. Effect of Clinical Site on System and Reference Agreement (sample table)

Site Number	Number of Paired Senseonics CGM and Reference	Percent within 20/20% Reference	Percent within 30/30% Reference	Percent within 40/40% Reference
1				
2				
3				

Table 21. Effect of Rate of Change on System and Reference Agreement (sample table)

System Rate of Change	Number of Paired Senseonics CGM and Reference	Percent within 20/20% Reference	Percent within 30/30% Reference	Percent within 40/40% Reference
<-2				
[-2,-1)				
[-1,1]				
(1,2]				
>2				

Table 22. Effect of Race or Skin Color on System and Reference Agreement (sample table)

Race and Skin Color Category	Number of Paired Senseonics CGM and Reference	Percent within 20/20% Reference	Percent within 30/30% Reference	Percent within 40/40% Reference
Race and Skin Color Category 1				
Race and Skin Color Category 2				
Race and Skin Color Category 3				

Table 23: CGM Satisfaction Survey Results (sample table)

Survey Questions	Agree Strongly (N/%)	Agree (N/%)	Neutral (N/%)	Disagree (N/%)	Disagree Strongly (N/%)
Question 1					
Question 2					
⋮					
Question N					

Table 24. Effect of Medications (sample table)

Class of Medication	Subjects Taking Medication	MARD with Medication [mean (SD) / n]	MARD with No Medication [mean (SD) / n]	P-value
Diabetes Medication				
Thyroid Medication				
Hypertension Medication				
Cholesterol Medication				

Table 25. Calibration Stability (sample table)

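### As assigned, the dominant-arm contrast in SAP Table 19 cannot be separated from transmitter generation, arm side and primary/secondary role in right-handed subjects

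*SAP*

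**What the plan says.** SAP 6.10.1.23 plans the analysis in one sentence: "Sensor Agreement will be stratified by dominant arm and examined to determine whether there is any evidence of differences". The Table 19 shell in Appendix 1 has a row for the dominant arm and a row for the other, with the number of pairs and the percentages within 20/20%, 30/30% and 40/40% of reference. It has no column for transmitter, firmware, side or handedness.

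SAP section 3 (and Protocol 3.3.1) fixes hardware by side. Two-sensor subjects have one sensor in each arm, "with the left sensor linked to a Gen 1 transmitter, and the right sensor linked to the Gen 2 transmitter". For the dexamethasone subset, "These subjects will only have one sensor inserted in the left arm, which will be linked to the Gen 1 transmitter". SAP 4.3 states "Subjects will not be randomized", and nothing in either document balances side against handedness. Handedness is recorded at screening (Protocol 4.1: "Demographics- including age, gender at birth, race/ethnicity, dominant hand, and BMI"), but no expected or target split is given.

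The two systems also differ in role. Under Protocol 1.1.2 and 4.2.5, Gen 1 is the primary system, calibrated by the subject and displaying glucose. Gen 2 is secondary, logs data only and displays nothing. SAP 4.2.1 defines three configurations: Gen 1 with study firmware, Gen 2 with study firmware and Gen 2 with updated firmware. Table 19 does not say which Gen 2 version it would use.

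**The concern.** The section asks whether agreement depends on wearing the sensor in the dominant arm. In right-handed subjects the two arms being compared also differ in transmitter generation, side of the body and role in the system. A gap between the rows could come from any of these. Equally, a real dominance effect could be offset by a hardware difference in the other direction and go unseen. Left-handed subjects have the opposite pairing, so pooling them dilutes the problem but does not remove it. A reader given only the two rows could not tell which explanation applies.

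The SAP itself treats the configurations as possibly different, since it reports endpoints separately for each of them.

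**Working it through.** **Inputs from the documents**
- Subjects inserted and subset size, SAP 4.4: "36 subjects will be inserted with either one Sensor (dexamethasone sub-group of 6 to 9 subjects) or two Sensors". So 27 to 30 subjects have two sensors.
- Sensors expected to supply pairs, Protocol 11.1.4: "Estimates based on 66 sensors".
- Hardware by side: SAP section 3.

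**Assumptions not in the documents**
- Share right-handed, h = 0.80 to 0.95 (5-20% left-handed), the same in one-sensor and two-sensor subjects.
- Equal numbers of pairs per sensor.
- No transmitter switches (relaxed in the last step).

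**Reproducing the plan's figure.** With 6 one-sensor subjects, 6 + 2 × 30 = 66 sensors, as stated: 36 left (Gen 1) and 30 right (Gen 2). With 9, the count is 9 + 2 × 27 = 63: 36 left and 27 right. The 66 shows that both arms are expected to contribute.

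**Right-handed subjects.** As assigned, all dominant-arm sensors are Gen 2 and all non-dominant-arm sensors are Gen 1, so the overlap with hardware is complete.

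**Pooled Table 19.** With n2 two-sensor subjects:
- Gen 2 share of the dominant row = n2·h / [n2·h + 36(1−h)]
- Gen 2 share of the non-dominant row = n2(1−h) / [n2(1−h) + 36h]

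If D is a true dominance effect and H the Gen 2 minus Gen 1 difference, the crude contrast is D + H × (first share − second share). For n2 = 30 and h = 0.90 the shares are 27.0 / (27.0 + 3.6) = 0.882 and 3.0 / (3.0 + 32.4) = 0.085, so 0.80 of H passes through.

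| h | n2 | Gen 2 share, dominant | Gen 2 share, non-dominant | Fraction of H passed on |
|---|---|---|---|---|
| 0.80 | 30 | 0.769 | 0.172 | 0.60 |
| 0.90 | 30 | 0.882 | 0.085 | 0.80 |
| 0.95 | 30 | 0.941 | 0.042 | 0.90 |
| 0.80 | 27 | 0.750 | 0.158 | 0.59 |
| 0.90 | 27 | 0.871 | 0.077 | 0.79 |
| 0.95 | 27 | 0.934 | 0.038 | 0.90 |

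The dominant row is thus 75-94% Gen 2 and the non-dominant row 83-96% Gen 1. The fraction is zero only at h = 0.50. The documents give no value for H, so I do not convert the fraction into percentage points.

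**Holding the configuration fixed.** Every assigned Gen 1 sensor is in a left arm. Within Gen 1, dominant versus non-dominant is therefore left-handed versus right-handed people: 36 × 0.05 = 1.8 to 36 × 0.20 = 7.2 subjects, against 34.2 to 28.8. Within Gen 2 the roles reverse, with 27 × 0.05 = 1.35 to 30 × 0.20 = 6 left-handed subjects. Among right-handed subjects alone, no within-configuration contrast exists as assigned.

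**Transmitter switches.** Protocol 5.10 moves the Gen 1 transmitter to the other arm after suspected failure of the primary sensor. If 5-15% of right-arm pairs came after such a switch (assumed), the Gen 2 share of the dominant arm in right-handed subjects would still be 95-85%.

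**The case against.** The best defence is SAP 4.2.3, which says the exploratory endpoints will also be calculated under the three configurations and points to section 6.10, where the dominance analysis sits. On that reading Table 19 would also be run per configuration, and pooling is an inference from the shell, not a stated plan. That much stands. But the list in 4.2.3 does not name the dominance analysis and Appendix 2 has no dominance table. Even if done, the split would hold hardware constant only by comparing a handful of left-handed people with the right-handed majority.

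It is also fair to say that the analysis is exploratory, that only descriptive statistics are planned, and that no hypothesis is attached. All of that stands and limits the consequence.

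A reader might go further and infer that the Table 19 effect simply is a Gen 2 versus Gen 1 effect. The documents do not support this, for three reasons. The pairing is not invariable, because Protocol 5.10 provides for switches. Side and primary/secondary role differ along with hardware. A true dominance effect may also be present, so the factors are inseparable and none of them is shown to be the cause. Nor do the documents plan a claim that insertion in either arm is equivalent.

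**Conclusion.** The point holds as a limit on interpretation. In right-handed subjects the dominant-arm contrast cannot, as assigned, be separated from transmitter generation, side and role; data collected after a Protocol 5.10 switch are the exception. If Table 19 is filled as drawn, about 59-90% of any Gen 2 minus Gen 1 difference in agreement would appear in the dominance contrast. That range rests on the assumed 5-20% left-handed share and on equal pairs per sensor, and it describes initial assignment. Whether a hardware difference exists, and in which direction, cannot be known from the documents. MARD is unaffected. This is a problem of one exploratory table that could be misread, and it is inexpensive to prevent.

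**What to change.** In SAP 6.10.1.23:
- Split Table 19 by transmitter/firmware configuration and by handedness, with subject and pair counts in every cell.
- Name the firmware version used for the Gen 2 readings.
- Show pairs collected after a Protocol 5.10 switch separately.
- State that dominance cannot be separated from transmitter and side in right-handed subjects, and that no dominance conclusion will be drawn from the pooled rows.

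As supporting description, the within-subject dominant-minus-non-dominant difference in two-sensor subjects, from pre-switch pairs, may be shown separately for right-handed and left-handed subjects. With H now standing for the combined hardware, side and role difference, it estimates D + H in the first group and D − H in the second. Their simple average isolates D only if D and H are the same in both groups. Averaging should therefore be optional, with that assumption and the left-handed count stated. It gives half the weight to very few people: in units of the within-subject SD of the difference, its standard error is 0.5 × √(1/1 + 1/26) = 0.51 with 1 left-handed subject of 27, and 0.5 × √(1/6 + 1/24) = 0.23 with 6 of 30.

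The cost is SAP wording and one table shell, since dominant hand is already collected. The downside is that the left-handed cells will be very small, about 1 to 6 two-sensor subjects under the assumed range, so the revised table may show little beyond the limitation itself.
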